The goal of the project is to dampen the intensity and frequency of opioid prescribing and to increase awareness and use of medication assisted therapy for persons with opioid use disorder through a cluster randomized trial. Overdose notification letters (See Appendix 2 and 3) will be sent to primary care clinicians randomized to the experimental study arm and meeting inclusion criteria at AltaMed Health Services or Northwestern Medicine. Both letters will include "if/when/then" language which advises the clinician to keep the letter's recommendations close when their next patient presents with pain. Clinicians notified of their patient's overdose will be compared to a control group receiving guideline education and no notification of their patient's overdose (Appendix 6). To quantify the effect of the notification letter, we will measure the change in clinician weekly milligram morphine equivalent (MME) prescribed to all of their patients in 6-month periods before and after receiving overdose feedback letters. The secondary outcomes include the change in proportion of patients prescribed at least 50 daily MME, buprenorphine referrals for medication assisted therapy, and access rates for referral links included in the letter.

Because the letters include patient identifying information linked to outpatient prescribing records, we requested a HIPAA waiver of authorization to match outpatient records to mortality and non-fatal overdose records. The research could not feasibly be conducted if research participants' authorization were required. AltaMed will release information under the auspices of a waiver of HIPAA authorization. USC and AltaMed have a fully executed Business Associates Agreement, Memorandum of Understanding and Data Use Agreement; Northwestern and IDPH and USC and Northwestern have a fully executed Data Use Agreement. AltaMed and Northwestern will cede to the County IRB as the IRB of record for this study.

To create the list of overdose patients for whom opioids were prescribed, outpatient records will be linked to the emergency department and, in the case of Northwestern patients, IDPH death records. Overdose data will be linked with outpatient records using matching software that complies with institutional security and privacy standards at IDPH and Los Angeles County. Where an existing direct link code is available (e.g. MRN), we will use the code.

Primary hypotheses:

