HIPAA Limited Data Set. At the conclusion of the study period, each health system will prepare a HIPAA limited data set for analysis. The data set will include dates of overdose events, post-intervention opioid prescribing, and unique study identifiers. Study assignment, physician notification information, and overdose data from Los Angeles County Department of Public Health will be de-identified retaining unique study identifiers. Data will be transferred to USC Schaeffer Center HIPAA data enclave for analysis. No USC study personnel will have access to any patient identifying information. Links between identified data and study identifiers will be destroyed at the conclusion of the analysis.

C. List of Experimental Procedures to be Employed

a) List and detail risks:

- Mitigation of risk to participating physicians
 - Letters are a normal aspect of quality review. Letters notifying clinicians of a fatal overdose are mandated in Los Angeles County. [see LA County Board of Supervisors Meeting <https://youtu.be/hBefHyAL5I8>]. Therefore, risks faced by participants do not exceed that of normal clinical practice. We will take every precaution to mitigate risk to participating clinicians by keeping this disclosure private. All correspondence will be private and conducted through delivery using one of the following approaches: 1) US Postal Service, 2) institutional email, or 3) Epic inbox message, and will not be shared outside of the study.
- Mitigation of risk to patients
 - Risk of correspondence adds no additional risk compared to what is already being sent in the mail or by email (such as prior authorization letters by insurers or billing). Further, the HIPAA conduit exception allows HIPAA-covered entities to use the US Postal Service, institutional email, and Epic inbox messaging for the transmission of personal health information. US Letters and email are private and tampering with private mail is a federal offense.
 - The NIH has established a Data and Safety Monitoring Board for this study. The board consists of individuals with expertise in opioids, overprescribing, biostatistics or research methods. When notified of an unanticipated event following the intervention, the board will convene and make a decision as to whether the study should continue.
 - A potential risk is an adverse event, defined by the CDC as an abrupt

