discontinuation of opioids for persons whose most recent prescription exceeds 49 MME daily dose; or as reported to study staff (10).

If there is a significant difference in the prevalence of these adverse events or overdoses between the treatment and control groups, the differences will be reported to the Data and Safety Monitoring Board and in the publication of the study results. *It is important to note that prior quality evaluations of these letters observed no additional risk of abrupt changes to opioid prescribing upon receipt of a letter (<https://pubmed.ncbi.nlm.nih.gov/30093595/>).*

- Management of overdose and prescribing data poses no more than minimal privacy risks. USC, health systems and IDPH comply with all local and federal security regulations protecting privacy. Identified patient data will be destroyed after the notifications have been prepared. A HIPAA Limited Data Set that includes outpatient prescribing records, overdose events, and notification status will be transferred to USC for data analysis in USC's HIPAA compliant enclave.

b) Experimental Procedures:

Randomization and Allocation. Overdose clusters are the units of randomization in this study. A cluster consists of all clinicians who prescribed one or more of the included scheduled drugs to the patient in the year prior to the overdose. Overdose clusters will be randomized to the overdose notification group or the control group, stratified by the health system which defines the cluster in the year prior to the overdose event.

Allocation will be concealed until after the study groups are assigned. Clinicians who practice at multiple clinics will be assigned to the clinic at which the majority of their visits occurred in the year prior to the overdose event. If clinicians belong to more than one cluster (have multiple patients with opioid-related overdoses), they will be randomly assigned to one of those patients and placed in the corresponding study group. If clinicians belonging to more than one cluster are randomized to the intervention group, they will only receive an overdose notification regarding the one patient to whom they were randomly assigned.

Intervention. Clinicians in the intervention group receive a letter notifying them of their patient's fatal or non-fatal overdose. As described above, we will identify overdoses from electronic health record data from emergency departments and state vital records.

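### The protocol promises to report the by-arm comparison of abrupt discontinuation and overdose if the difference is significant, and promises nothing if it is not

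*Combined protocol and SAP*

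**What the plan says.** Section C.a (List and detail risks) names abrupt stopping of opioids, in patients whose last prescription was above 49 MME a day, as a potential adverse event, together with events reported to study staff. It then sets the reporting rule, whose condition reads: "If there is a significant difference in the prevalence of these adverse events or overdoses between the treatment and control groups". When that condition is met, the protocol undertakes to take the comparison to the monitoring board and into print. Significance is not defined: no test, alpha level or sidedness is given.

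The same section gives the monitoring board a second route: "When notified of an unanticipated event following the intervention, the board will convene and make a decision as to whether the study should continue".

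The synopsis in Section B.a lists other endpoints: "The secondary outcomes include the change in proportion of patients prescribed at least 50 daily MME, buprenorphine referrals for medication assisted therapy", plus use of the referral links in the letter. Neither abrupt discontinuation nor overdose is among them. Section D (Statistical Analysis Plan) models opioid volume and high-dose prescribing only. On the analysis file, Section B.f says: "The data set will include dates of overdose events, post-intervention opioid prescribing, and unique study identifiers". That file is prepared when the study period ends.

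**The concern.** A significance test is a poor filter for harms. It makes reporting depend on the p-value, so readers cannot tell a difference that was small from one that was estimated too imprecisely to judge. Whether to show a non-significant difference becomes a choice made after the data are seen.

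The point matters more here for three reasons. The letters (Appendices 2 and 3) encourage less prescribing and tapering of high doses, so abrupt discontinuation is the foreseeable harm in the direction the intervention pushes. The consent waiver (Section E) rests on minimal risk. And Section C.a cites earlier evaluations as having found no additional risk of abrupt change, so an unreported null result could be taken as confirmation.

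**Working it through.** **1. The text.** The plan contains no harms figure to reproduce, so the main check is to set the commitments side by side.

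| Place | Commitment | Comparison by arm? | Condition |
|---|---|---|---|
| C.a, adverse events and overdoses | Report to board and in publication | Yes | A significant difference |
| C.a, monitoring board | Board convenes and decides on continuation | No | Notice of an unanticipated event |
| B.a, secondary outcomes | Prescribing, referral and link use | Harms not listed | None |
| D, analysis plan | Models for pills and high-dose prescribing | Harms not analysed | None |

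If the harm comparison is significant, both reports are promised. If it is not, no row promises either. The unanticipated-event route does not fill the gap, because an excess of a foreseen event need not trigger it and it yields no table by arm.

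**2. Could a true harm miss significance? (Illustration only.)** None of these inputs is in the documents: 1:1 allocation, two-sided alpha 0.05, n = 200 or 1,000 at-risk patients per arm, design effect 1.5, control risk p1 of 1% to 5%.

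- n_eff = n / 1.5
- se0 = √[2p̄(1−p̄)/n_eff], where p̄ = (p1+p2)/2
- se1 = √[(p1(1−p1)+p2(1−p2))/n_eff]
- power = Φ[(p2 − p1 − 1.96·se0)/se1]

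Lowest cell for a doubling, 1% vs 2%, n = 200: n_eff = 133.3, se0 = 0.01489, se1 = 0.01487. Power = Φ[(0.0100 − 0.0292)/0.01487] = Φ(−1.29) = 0.099.

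Highest cell, 5% vs 10%, n = 1,000: n_eff = 666.7, se0 = 0.01443, se1 = 0.01436. Power = Φ[(0.0500 − 0.0283)/0.01436] = Φ(1.51) = 0.935.

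| Control vs letter arm | n = 200 | n = 1,000 |
|---|---|---|
| 1% vs 2% | 0.099 | 0.323 |
| 2% vs 4% | 0.158 | 0.572 |
| 3% vs 6% | 0.218 | 0.753 |
| 5% vs 10% | 0.340 | 0.935 |
| 3% vs 4.5% | 0.094 | 0.302 |
| 5% vs 7.5% | 0.132 | 0.470 |

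**3. A second set of assumptions, starting from the documents' totals.** Section B.b gives 134 + 387 = 521 clinicians and 17,674 + 12,552 = 30,226 patients, or about 58 per clinician. These are ceilings, since only clinicians with an overdose patient are eligible. Suppose 10% of those patients are at risk (5.8 per clinician) and the ICC is 0.05. The design effect is 1 + 4.8 × 0.05 = 1.24, and the effective number per arm is 30,226 × 0.10 / 2 / 1.24 ≈ 1,219. Power to detect a doubling is then 30% at a 0.5% base, 53% at 1%, 83% at 2% and above 99% at 5%.

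**4. What a non-significant result could hide.** Take a hypothetical observed 2% vs 3% with 1,000 per arm and design effect 1.5. The standard error is √[(0.0196 + 0.0291)/666.7] = 0.0085. The difference is 1.0 percentage point, with 95% interval 1.0 ± 1.7, that is −0.7 to +2.7. The rule would not require this to be reported, yet the upper limit is more than a doubling of the 2% risk.

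**The case against.** The sentence in Section C.a is a promise to report, not a bar on reporting. A reader might infer that differences go to the board and into print only if statistically significant. The text says neither *only* nor *statistically*. The statistical sense is the natural one for a difference in prevalence between arms, but what the documents support is that there is no commitment to report otherwise. If clinical importance was meant, no threshold is given. A reader might also infer that this is the sole safety route. It is not, since the unanticipated-event route carries no significance condition.

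A reader might further infer that the trial is underpowered for harms. The documents do not show this. The power figures rest wholly on assumptions, and at a 5% base with 1,000 per arm a doubling would usually be detected.

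Two practical objections also stand in part. First, the analysis file is prepared at study end and the intervention lasts one day, so a comparison from that file would come too late to change exposure; the effect falls mainly on the completeness of the publication. Second, data capture is uneven. Los Angeles fatal overdoses are excluded, Los Angeles records of patients without an overdose are destroyed, and the Northwestern non-fatal search is a single extract at the start. The documents do not say clearly that overdoses after the letter are captured. That limits what can be reported, but it limits the promised significance test equally, so it is no reason to keep the condition.

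**Conclusion.** The point holds as a gap in the reporting commitment. One conditional sentence governs both the board report and the publication, and nothing else in the documents supplies a by-arm report of harms when the difference is not significant. This follows from the text and needs no numerical assumption.

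The size of the consequence is open. On the assumed grid, power to detect a doubling ranges from about 10% to about 93%, and to detect a 1.5-fold increase from about 9% to 47%. A true harm could therefore fall outside the rule, but the documents do not establish that it would. The primary analysis is unaffected. The change should be made before the analysis.

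**What to change.** Replace the conditional sentence in Section C.a with: *Counts, denominators and the between-arm difference with a cluster-robust 95% confidence interval for abrupt discontinuation and for overdoses captured by the study's data sources (Los Angeles fatal overdoses are not captured) will be reported to the DSMB and in the publication, regardless of statistical significance.* Carry other reported adverse events, which the present rule also covers, in the same table by arm.

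Three additions make this workable. Section D should name the analysis. The protocol should state when the comparison goes to the board. The sponsor should also confirm which overdoses after the letter are captured at each site, and give an operational definition of abrupt discontinuation, since the present text states the population but no time window or criterion.

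The cost is one sentence and one extra table. A significance test already needs the same counts and denominators, so the wording adds no data requirement of its own, though confirming capture may take some work. The downside is that a small non-significant difference may need explaining in the publication.

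### By-arm reporting of abrupt opioid discontinuation and overdoses is promised only if the difference is significant, with no test or alpha stated, so a real excess resting on few events could go unreported

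*Combined protocol and SAP*

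**What the plan says.** Section C.a (List and detail risks) names the expected harm to patients. It is the abrupt "discontinuation of opioids for persons whose most recent prescription exceeds 49 MME daily dose; or as reported to study staff (10", the last figure being a reference number. The next paragraph sets the reporting rule: "If there is a significant difference in the prevalence of these adverse events or overdoses between the treatment and control groups", then "the differences will be reported to the Data and Safety Monitoring Board and in the publication of the study results".

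The same section gives one other route to the board: "When notified of an unanticipated event following the intervention, the board will convene and make a decision as to whether the study should continue".

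Section D (Statistical Analysis Plan) gives Eq. 1 for pills prescribed and Eq. 2 for high-dose prescribing, offered as the model for the secondary outcomes. Neither is set out for abrupt discontinuation or overdose. Section C.b adds a point that any harms comparison must respect: "Overdose clusters are the units of randomization in this study".

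On data, section B.f (HIPAA Limited Data Set) says "The data set will include dates of overdose events, post-intervention opioid prescribing, and unique study identifiers" and "Study assignment, physician notification information, and overdose data from Los Angeles County Department of Public Health will be de-identified retaining unique study identifiers". Section C.a repeats the plan: "A HIPAA Limited Data Set that includes outpatient prescribing records, overdose events, and notification status will be transferred to USC".

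**The concern.** The rule makes the reporting of harm depend on a significance test, and the test is undefined. No method, alpha, sidedness, denominator or allowance for clustering is stated, so two analysts could follow the sentence faithfully and disagree on whether a difference must be reported.

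When events are few, a non-significant difference is weak evidence that no harm occurred. The letters advise clinicians to avoid opioids for chronic pain and to bring high doses below 50 MME, with slow tapers. Abrupt stopping above 49 MME is what overshooting that advice would look like, so it is the harm on which the board and readers most need the counts.

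The unanticipated-event route does not fill the gap. It starts from notice of an event and supplies no comparison by arm, and a harm named in advance is not plainly unanticipated.

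**Working it through.** **Inputs.** The plan states no event rate, power, test or alpha for harms, so there is no figure of its own to reproduce. Assumed: equal arms, independent Poisson counts, a true doubling in the letter arm, and a two-sided exact conditional test at 0.05.

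**Formula.** Let the expected counts be m (control) and 2m (letter). Given D events in total, the letter-arm count is Binomial(D, 1/2) if there is no difference and Binomial(D, 2/3) under a doubling. The chance of a significant excess is the sum over D of Poisson(D; 3m) × P(letter count lies in the upper rejection region | D, 2/3). For a design effect of 1.5 (also assumed), both expected counts are divided by 1.5.

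| Expected events, control v letter | Reaches p<0.05 | With design effect 1.5 |
|---|---|---|
| 5 v 10 | 17.8% | 10.5% |
| 10 v 20 | 37.4% | 24.5% |
| 20 v 40 | 70.2% | 50.5% |
| 40 v 80 | 95.0% | 82.8% |

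**The unstated alpha matters.** With the total fixed at D and a true doubling, the chance at alpha 0.01, 0.05 and 0.10 is 17%, 43% and 59% for D = 30, and 37%, 61% and 71% for D = 50. With D of 5 or fewer, significance at 0.05 is impossible: 5 v 0 gives p = 2 × 0.5^5 = 0.063.

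**What observed splits would look like (letter v control).** The interval is the exact binomial interval for the letter share s, converted to a ratio by s/(1 − s).
- 12 v 10: ratio 1.20, 95% CI 0.48 to 3.10, p=0.83. Not significant, yet a doubling is not excluded.
- 20 v 10: ratio 2.00, 95% CI 0.89 to 4.78, p=0.099. Not significant, so outside the commitment.
- 40 v 20: ratio 2.00, 95% CI 1.14 to 3.61, p=0.013. The same ratio, now inside it.

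**Exaggeration among differences that pass.** With a true ratio of 2.0, the median observed ratio among significant excesses is 2.89 at 10 v 20, 2.24 at 20 v 40 and 2.03 at 40 v 80. It matters only when events are few.

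**Can the documents fix the row?** Section B.b lists 17,674 + 12,552 = 30,226 patients, or 15,113 per arm if every clinician were enrolled. Only clinicians with an overdose patient are eligible, and their share of patients is not given. Assume 10% of patients are above 49 MME:
- 5% stop abruptly, all enrolled: 15,113 × 0.10 × 0.05 = 75.6 control events; a doubling is significant in 99.9% of cases.
- 5% stop, 50% enrolled: 37.8 events; 94%.
- 10% stop, 20% enrolled: 15,113 × 0.20 × 0.10 × 0.10 = 30.2 events; 88%.
- 5% stop, 20% enrolled: 15.1 events; 56%.
- 5% stop, 10% enrolled: 7.6 events; 28%.

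These are before any design effect. The denominator is itself uncertain: the Northwestern count is of chronic-therapy patients, while the event definition has no chronic-use limit. The spread from 28% to 99.9% shows that the row cannot be settled from the documents.

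**The case against.** The strongest reply is that the sentence says what happens if a difference is significant and does not say that other differences will be withheld. That stands. A reader might infer that the plan suppresses non-significant harms, and the documents do not support it. What they support is that no such reporting is promised.

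The reply on the board is also partly right. The NIH set the board up, and its procedures need not appear in this protocol, so one cannot conclude that it will see no by-arm data. Moreover, the analysis data set is prepared when the study period ends and the intervention is a one-day letter, so a table built from it would reach the board after exposure. The practical gain is therefore mainly in the publication, with a complete final account for the board. It remains true that the protocol should not set a weaker standard than whatever the board uses.

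A third reply is that overdose counts may not be free. This stands too. Under section B.f, Northwestern non-fatal overdoses come from a single extract at the start of the study, Los Angeles data on patients without an overdose event are destroyed, and Los Angeles fatal overdoses are excluded. The planned data set holds overdose dates, but nothing says that these extend past the letter. The overdose part of any fix has to be limited accordingly.

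**Conclusion.** The point holds as a gap in what is promised. The only stated commitment to report these harms by arm depends on an undefined significance test, and with few events that test would often miss a true doubling: about 18% reach significance at 5 v 10 expected events and 37% at 10 v 20, but 95% at 40 v 80. These figures assume equal arms, Poisson counts and a two-sided 0.05; clustering lowers them.

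A reader might go further and state what share of true harms the rule would hide. The documents do not allow that, because event rates and the enrolled share are not given and plausible inputs lead to opposite answers. If events are numerous, the condition hardly matters.

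The primary analysis is unaffected. The change is still worth making, because the harm is one that the protocol names itself and the remedy is a wording edit.

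**What to change.** Replace the conditional sentence in section C.a with:

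> Counts by arm of abrupt discontinuation (most recent prescription above 49 MME daily dose), with numbers at risk and 95% confidence intervals that allow for clustering by overdose cluster, will be reported to the Data and Safety Monitoring Board and in the publication whether or not the difference is significant. Overdoses after the letter date will be reported in the same way, by health system, to the extent that the planned data sources capture them, stating which sources cover fatal or non-fatal events.

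The present sentence also covers events reported to study staff; listing these separately by arm would keep the replacement from narrowing its scope.

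The cost is a short protocol edit with notification to the IRB. For discontinuation, the present rule already requires counts by arm to judge significance, and the limited data set is planned to hold prescribing records and study assignment. For overdoses, the wording asks only for what the planned sources hold, so no new linkage is required. No early look is asked for, and the letters, the unanticipated-event trigger and the primary analysis stay as they are. The downside is that chance differences in small counts will be visible; they should be presented descriptively, with their intervals.
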